2.2.2 Dose Rationale

The proposed initial doses of 1, 2 and 5 µg for this FIH clinical study were chosen based on the PS levels contained in marketed PS conjugate vaccines and the ASP3772 nonclinical pharmacology and toxicology studies.

The 3 currently licensed pneumococcal conjugated vaccines vary in the number of serotypes they contain, the carrier proteins used and the methods of conjugation employed. The 7-valent formulation (Pfizer's Prevnar 7/Prevnar 7) with all serotypes conjugated to diphtheria toxoid mutant (CRM197), using a reductive animation conjugation method, was first licensed in the year 2000. The 10-valent formulation (GlaxoSmithKline Biologicals' Synflorix), with 8 serotypes conjugated to Protein D, a recombinant non-lipidated form of a highly conserved 40 kDa cell-surface lipoprotein of non-typeable *Haemophilus influenzae*, serotype 18C conjugated to tetanus toxoid and serotype 19F conjugated to diphtheria toxoid via bifunctional spacer, was licensed in Europe in 2009. The 13-valent formulation (Pfizer's PCV13/PCV13), with all serotypes conjugated to CRM197 using reductive animation, was licensed in 2010. In addition, Merck initiated the development of a 15-valent formulation (V114), using the PS dose ranges used previously by the commercially available pneumococcal conjugated vaccines. In all of these cases, the PS doses ranged from 1 μg to 4.4 μg for each of the serotypes. A nonclinical immunogenicity study with ASP3772 and PCV13 at one-tenth of the human PCV13 dose for each PS showed that ASP3772

serotype-specific responses to ASP3772 were comparable to those elicited by PCV13 for the 13 serotypes in common between the vaccines. For the 11 noncommon serotypes, there was a robust response elicited in rabbit for ASP3772 and no response for PCV13. In the toxicology study in New Zealand White rabbits, ASP3772 was administered at 5 µg of each of the 24 PS every 2 weeks, for a total of 5 intramuscular injections (5 cycles). The findings were mild in nature, and monitorable and reversible.

The above information, coupled with the literature showing successful translation between the rabbit immunogenicity studies and human efficacy for pneumococcal vaccines, support the position that ASP3772 has the potential to be clinically effective at the proposed doses (1 μ g, 2 μ g and 5 μ g).

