4.4 Blinding

4.4.1 Blinding Method

This is an observer-blind study since the comparator has a unique syringe that the sponsor cannot duplicate. Subjects will be randomized at a 3:1 ratio (ASP3772:comparator vaccine PCV13) in a blinded fashion such that the investigator, clinical staff, nor the subject will know which agent is being administered. Only the pharmacist and designated staff, including the person(s) injecting the vaccine will be unblinded to study vaccine. The syringes will be masked prior to dosing to maintain the blind for subjects and all other personnel. The details regarding study blinding will be described in the pharmacy manual. The randomization number will be assigned based on information obtained from the IRT. The study will be unblinded to the investigator after the database lock.

The safety and tolerability data for dose escalation by the DEC will be reviewed under blinded conditions. If there are AEs that meet the criteria that could prohibit dose escalation, (i.e., a SAE, an AE of severe intensity, or 2 or more subjects experience a reactogenicity event of grade 3 or higher intensity), the study vaccine assignment for these subjects will be revealed to determine if these events are related to ASP3772. If 10% or more of the subjects within a cohort experience the same or related AE, the study vaccine assignment for those subjects will be revealed to determine if there is an imbalance in unsolicited AEs between ASP3772 and PCV13. The DEC can request the study vaccine assignment for 1 or more subjects.

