5.3.1 Immunological Response

Considering its mechanism of action, ASP3772 is expected to induce the immune response to pneumococcal PS and carrier proteins, the antigens present in ASP3772. Blood samples to assess immunogenicity will be collected as indicated in the Schedule of Assessments [Table 1, Table 2 and Table 3]. Immunogenicity assessments will be performed from blood samples collected at the dosing visit (day 1) prior to study immunization and at the 7-day and 30-day follow-up visits. Immunogenicity data will be provided to the investigative site when available.

Immunogenicity of ASP3772 will be evaluated by measuring serotype-specific anticapsular IgG antibody concentrations by multiplex direct Luminex immunoassays and OPA titers against the 24 vaccine serotypes in serum samples. OPA measures the functional killing activity of antibodies against the pneumococcal serotypes. In addition, pneumococcal carrier protein (SP1500+0785)-specific immune response will be assessed by measuring specific IgG in serum and activity against non-vaccine serotypes. Thelper 17 cells (Th17) response to SP1500+0785 will be evaluated by measuring interleukin (IL)-17.

blood mononuclear cells (PBMCs) as exploratory assessments.

Details on sampling, processing and storage will be described in the laboratory manual. Samples will be shipped on dry ice to a designated contract research organization (CRO) for the analyses.

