- g. Body temperature, blood pressure and pulse rate will be assessed in a sitting position. At the dosing visit, body temperature, blood pressure, pulse rate and respiratory rate will be assessed predose at approximately 30 min and 1 hour postdose. Predose vitals should be collected close to the immunization and should not be more than 30 minutes prior to the dose administration. Body temperature will be collected by the subject daily through day 7 following the study immunization.
- h. Perform test for hematology (hemoglobin, hematocrit, erythrocytes, leukocytes, differential WBC, platelets), biochemistry (sodium, potassium, calcium, chloride, glucose, total cholesterol, triglycerides, blood urea nitrogen, creatinine, total protein, albumin, c-reactive protein), coagulation profile (prothrombin time, activated partial thromboplastin time, fibrinogen), hepatic profile (alkaline phosphatase, aspartate transaminase, alanine transaminase, γ-glutamyltransferase, total bilirubin, lactate dehydrogenase), urinalysis (using dipstick - protein, glucose, pH, blood, leukocytes, urobilinogen, bilirubin, ketones, nitrite, urine microscopy [optional]).
- i. CCI [REDACTED]
- j. Immunogenicity data will be provided to the investigative site when available to support decision-making for the standard of care.
- k. Sample collection to test for serum anti-biotin antibodies should be repeated at the day 180 visit if tested positive on day 30. Biotin levels will be measured in the same sample if the sample is positive for anti-biotin.
- l. All concomitant medications or therapies administered from the time the informed consent form (ICF) is signed through day 30 follow-up visit will be collected.
- m. Subject must be under direct supervision for the first 60 minutes following the injection. Local reactogenicity will be evaluated at 1 hour by site staff and entered into the electronic diary by the subject while on site. The subject will evaluate local and systemic reactogenicity symptoms except for joint pain/arthralgia as per Appendix B daily and record the results on an electronic diary daily through day 7 following the study immunization. On day 7, subject will be questioned if he/she experienced any other illness, which is not incorporated into the reactogenicity assessment, in the electronic diary.

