Stage 2 of the study is a dose-finding (sequentially higher doses), active-controlled, observer-blinded study with a 3:1 randomization (ASP3772:PCV13) in elderly subjects 65 to 85 years of age (Group 2). For Stage 2, Group 2 subjects the vaccine administrator will differ from the person evaluating reactogenicity to remove reporting bias for these events. Treatment assignment will also be unknown to the blinded study team.

After screening, PCV13 naïve subjects will be randomized within each cohort to receive ASP3772 or PCV13. Subjects randomized to ASP3772 will receive a single dose of ASP3772 administered as a 0.5 mL intramuscular (IM) injection on day 1, at 1 of 3 dose levels: 1, 2 or 5 µg of ASP3772 for Cohorts 4, 5 and 6, respectively. The subjects randomized to PCV13 will receive a single injection of the standard dose of PCV13.

Stage 2 will commence after the DEC has evaluated safety (including reactogenicity) data through 30 days from all cohorts in Stage 1. Dose escalation to Cohort 5 (intermediate dose, 2 µg) in Stage 2 will commence once the DEC has evaluated Stage 2 Cohort 4 (1 µg) safety (including reactogenicity) and tolerability through 7 days postimmunization. Dose escalation into Cohort 6 (high dose, 5 µg) in Stage 2 will commence once the DEC has evaluated Stage 2 Cohort 5. The DEC will review the data for each cohort in Stage 2, Group 2 in a blinded manner. The DEC Charter will provide details for revealing the treatment assignment for individual subjects to DEC members, if necessary. Randomization for Stage 2 subjects will be stratified by age (65 to 74 years of age and 75 to 85 years of age) to ensure there is a balanced number of subjects within each age cohort immunized with either ASP3772 or PCV13.

Safety and tolerability assessments including adverse events (AEs) will continue through 30 days postimmunization. Safety assessments for SAEs and MAAEs including PIMMCs and NOCDs will continue through day 180 postimmunization. Data will be collected in an observer-blinded manner (vaccine recipients and the site staff who are responsible for evaluation of any study endpoint will be unaware of which vaccine the subject received).

Serum samples to measure IgG and OPA will be collected prior to study vaccination on day 1 and postimmunization on day 30. The primary immunogenicity evaluation for dose finding is 30 days following the initial immunization.

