6.1.2 Secondary Endpoint(s)

Stage 1, Group 1:

Surrogate markers used to assess the immunological response on day 30 for the 13 serotypes common to ASP3772 and PCV13 are:

- Functional OPA activity for each serotype characterized by an OPA titer⁻¹ response expressed as the reciprocal of the serum dilution that causes a 50% reduction in the colony-forming units
- Pneumococcal serotype-specific anticapsular polysaccharide PS IgG for each serotype.

Summaries of immune response 30 days after immunization in adults 18 to 64 years of age will be provided for each serotype by treatment group (ASP3772 (1 µg, 2 µg, 5 µg) or PCV13) and stage. All adult subjects treated with PCV13 will be combined into a single group. To assess similarity between the 3 cohorts of PCV13 subjects, summaries will be provided by cohort for the PS IgG levels and the OPA titers.

Endpoints used to assess the immunological response on day 30 for the 11 serotypes unique to ASP3772 (2, 8, 9N, 10A, 11A, 12F, 15B, 17F, 20B, 22F, 33F) are:

- Geometric mean fold rise (GMFR) in anticapsular PS IgG at 30 days relative to pre-immunization
- Proportion of subjects with a ≥ 4 -fold increase in anticapsular PS IgG
- Functional OPA activity for each serotype characterized by an OPA titer⁻¹ response

Stage 2; Group 2:

Endpoints used to assess the immunological response on day 30 are:

- Functional OPA activity for each serotype characterized by an OPA titer⁻¹ response
- Pneumococcal serotype-specific anticapsular PS IgG for each serotype for the 13 serotypes contained in PCV13
- For each of the 11 serotypes unique to ASP3772, the GMFR in anticapsular PS IgG at 30 days relative to pre-immunization
- For each of the 11 serotypes unique to ASP3772, the proportion of subjects with a ≥ 4 -fold increase relative to baseline in anticapsular PS IgG for ASP3772 and PCV13-treated subjects

For Stage 2, Group 2 summaries will be provided by treatment group (ASP3772 (1 μ g, 2 μ g, 5 μ g) or PCV13) for all subjects age 65-85, for subjects 65-74 and for those 75-85. Subjects treated with PCV13 in cohorts 4, 5 and 6 will be combined into a single dose group and summarized by age (65-85, 65-74 and 75-85). To assess similarity between the 3 cohorts of PCV13 subjects, summaries will be provided by cohort for the PS IgG levels and the OPA titers.

In addition, for ASP3772, the following endpoints will be assessed.

- Dose response in the OPA titer⁻¹ for ASP3772
- Dose response in the PS IgG antibodies for ASP3772

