7.6 Interim Analysis

Safety data will be provided for DEC review after the sentinel subjects and after each dose cohort for the adult and elderly populations after the Day 7 visit for dose escalation decisions. Prior to initiating enrollment of the elderly subjects, the DEC will review the available data through 30 days post immunization in adult subjects. Details are provided in the DEC Charter.

The immunogenicity endpoint will occur 30 days after immunization. Once all subjects in Stage 1 have completed 30 days, there will be a database cut-off to conduct a formal analysis of the immunogenicity data. All data will be cleaned and the treatment assignment will be unblinded to Astellas. Treatment assignment will continue to be unavailable to the sites until after all subjects have completed the 180-day follow-up, all data has been cleaned and the database has been locked.

Similarly for subjects in Stage 2 once Stage 2 subjects have completed 30 days, there will be a database cut-off to conduct an interim analysis of the immunogenicity data. All data will be cleaned and the treatment assignment will be unblinded to Astellas. Treatment assignment will remain unavailable to the sites until after all subjects have completed the 180-day follow-up and the database has been locked.

In addition, there will be an expedited assessment of whether there is an immune response to ASP3772 in the Stage 1, adult subjects. The vendor responsible for analyzing the immunogenicity data will provide a file of the immunogenicity results with the patient numbers to an unblinded member of Bioanalytics team who will then add the treatment assignment and remove the subject numbers. The data will be sorted based on treatment assignment, which will further obscure the possibility of identifying the individual treatment assignment for an individual subject. Summaries of the IgG and OPA titers will be provided by ASP3772 dose and for combined Prevnar 13 subjects. The purpose of this exercise is to determine if any doses should be eliminated from the planned toddler study due to insufficient immunogenicity in the healthy adult population.

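### Immunogenicity results go to sites with no limit on timing, serotype or recipient, which conflicts with keeping sites blinded until Day 180 follow-up and database lock

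*SAP*

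**What the plan says.** **Release.** SAP Table 2, footnote j, and the matching footnote to Protocol Table 2 (both Group 2) state: "Immunogenicity data will be provided to the investigative site when available to support decision-making for the standard of care". Protocol 5.3.1 states: "Immunogenicity data will be provided to the investigative site when available". That sentence names no group, so it also covers the randomized adults in Stage 1 (Group 1).

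**Blinding.** SAP 7.6 says of Stage 2: "Treatment assignment will remain unavailable to the sites until after all subjects have completed the 180-day follow-up and the database has been locked". It has an equivalent sentence for Stage 1. Protocol 4.4.1 says: "The study will be unblinded to the investigator after the database lock". SAP 3.2 applies the observer-blind to vaccine recipients and adds that "the site staff who are responsible for evaluation of any study endpoint will be unaware of which vaccine the subject received".

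**When results exist.** SAP 7.6 plans that, once Stage 2 subjects have completed 30 days, "there will be a database cut-off to conduct an interim analysis of the immunogenicity data". SAP 3.3 places that cut after all Group 2 Day 30 visits.

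**What the results contain.** IgG and OPA are measured for all 24 serotypes. A listed endpoint in SAP 6.1.2 is "For each of the 11 serotypes unique to ASP3772, the GMFR in anticapsular PS IgG at 30 days relative to pre-immunization". Protocol Appendix 12.5 also lists antibody to SP1500+0785, the ASP3772 carrier protein, under immunogenicity.

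**The concern.** The blinding rule protects the assignment itself, while the release rule hands over data from which the assignment may be inferred. PCV13 contains neither the 11 additional serotypes nor the SP1500+0785 carrier. A rise across those serotypes between Day 1 and Day 30 therefore points to ASP3772, and a flat profile points to PCV13. The protocol's own animal data (2.2.2) show the expected contrast: "For the 11 noncommon serotypes, there was a robust response elicited in rabbit for ASP3772 and no response for PCV13".

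Safety is the primary objective. SAEs and MAAEs, including PIMMCs and NOCDs, are followed to Day 180. Under Protocol 5.5.1 and 5.5.3 the investigator decides whether an MAAE is a PIMMC or an NOCD and judges causality. Subjects report these events, possibly by telephone at Day 180. If either party can infer the vaccine, reporting, classification and causality after Day 30 may be affected by that knowledge.

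**Working it through.** The plan gives no figure on this point, so there is none to reproduce. The check has two parts.

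**1. The two rules side by side**

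| Question | Release rule | Blinding rule |
|---|---|---|
| When? | When available | After all 180-day follow-up and database lock |
| Which results? | Immunogenicity data, no serotype or assay excluded | Assignment withheld; results from which it can be inferred are not mentioned |
| To whom? | The investigative site | Not to sites, investigators, endpoint assessors or recipients |

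No release passage refers to the blinding rule, and neither blinding section mentions the release. SAP 7.6 does remove subject numbers for the expedited Stage 1 review, but no comparable step covers the release to sites. A site that follows the release rule literally can therefore breach the blinding rule.

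If a result reached the site at Day 30, 180 − 30 = 150 days of follow-up would remain. That is an upper limit, since assay and cleaning time come first.

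**2. How informative a profile would be (illustration only)**

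Inputs from the documents are the 11 non-PCV13 serotypes and the allocation of 99 to 33 per Group 2 cohort, so 99/132 = 75% receive ASP3772. The chance of a ≥4-fold IgG rise per serotype is an assumption: 30%, 50% or 70% after ASP3772, and 2%, 5% or 10% after PCV13.

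Call a subject ASP3772 if at least r of the 11 serotypes rise. Let s be the probability of that call after ASP3772 and f the probability after PCV13.

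- Correct overall = 0.75·s + 0.25·(1 − f)
- Probability that a flagged subject had ASP3772 = 0.75·s / (0.75·s + 0.25·f)
- Probability that an unflagged subject had PCV13 = 0.25·(1 − f) / [0.25·(1 − f) + 0.75·(1 − s)]

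Worked case: 30% against 5%, independent serotypes, r = 2.

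- s = 1 − 0.70^11 − 11·0.30·0.70^10 = 0.887
- f = 1 − 0.95^11 − 11·0.05·0.95^10 = 0.102
- Correct overall = 0.75·0.887 + 0.25·0.898 = 0.890

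Responses within one person are unlikely to be independent. The correlated rows therefore use a beta-binomial with parameters p(1 − ρ)/ρ and (1 − p)(1 − ρ)/ρ. The cut-off is the better of 2 and 3 for ρ = 0, and the best of 1 to 4 otherwise.

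| Rates, ASP3772 / PCV13 | ρ | r | s | f | Correct overall | Flagged: had ASP3772 | Unflagged: had PCV13 |
|---|---|---|---|---|---|---|---|
| 70% / 2% | 0 | 3 | 99.9% | 0.1% | 99.9% | >99.9% | 99.8% |
| 50% / 5% | 0 | 3 | 96.7% | 1.5% | 97.2% | 99.5% | 90.9% |
| 30% / 5% | 0 | 2 | 88.7% | 10.2% | 89.0% | 96.3% | 72.6% |
| 30% / 10% | 0 | 2 | 88.7% | 30.3% | 84.0% | 89.8% | 67.3% |
| 50% / 5% | 0.2 | 1 | 96.7% | 25.0% | 91.3% | 92.1% | 88.3% |
| 30% / 10% | 0.2 | 1 | 84.8% | 44.3% | 77.5% | 85.2% | 55.0% |
| 50% / 5% | 0.4 | 1 | 88.5% | 17.0% | 87.1% | 94.0% | 70.7% |
| 30% / 10% | 0.4 | 1 | 70.0% | 31.4% | 69.6% | 87.0% | 43.2% |

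Always guessing ASP3772 is right 75% of the time. In the last row the rule does worse than that overall. The profile is still informative there: a flag raises the probability of ASP3772 from 75% to 87.0%, and no flag raises that of PCV13 from 25% to 43.2%. Carrier-protein results are not modelled.

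**The case against.** A reader might infer that the plan does unblind sites before Day 180. The documents do not say so. No passage gives a release date, says that results are per subject, or names the assays sent. The rules can also be read together, with results becoming available to sites only after lock, and the pharmacy or laboratory manual may restrict release. This stands as a limit on the claim: early, per-subject release is an inference from the standard-of-care purpose and the Day 30 analysis. It does not remove the conflict, because neither document requires the benign reading.

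The timing is also uncertain. The Group 2 cut follows the last Day 30 visit of three sequential cohorts, so early enrollees may be near Day 180 by then. The number of exposed subjects cannot be stated.

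A reader might also infer that the primary safety endpoints as a whole are compromised. They are not. Reactogenicity ends at Day 7, and TEAEs are defined to Day 30. Appendix 12.5 schedules the IgG, OPA and anti-SP1500+0785 samples only at Day 1 and Day 30, so most of those events are recorded before any result exists. SAP 7.5.1 even labels its MAAE, PIMMC and NOCD tables as TEAEs. What remains is SAE, MAAE, PIMMC and NOCD assessment after Day 30. That includes NOCD status, which depends on non-resolution at the follow-up call, and any later revision of causality.

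Finally, a reader might conclude that the arm is almost fully readable. That needs high response rates or near-independent serotypes. The contrast cited from the protocol is in rabbits, and under strong correlation and a modest contrast accuracy falls below the 75% guess.

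**Conclusion.** The release rule and the blinding rule conflict in the current text of both documents, and this conclusion does not depend on the illustration. Per-subject results released before lock would be informative about the arm for many subjects. Across the cases shown, 69.6% to 99.9% are classified correctly against a 75% baseline, under response rates and correlations that are assumed throughout.

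The exposure is confined to Day 30 to Day 180 SAE, MAAE, PIMMC and NOCD reporting, classification and causality in Groups 1 and 2. For Group 1 it rests on Protocol 5.3.1, since the Group 1 schedule shows no such footnote in the readable text. Group 3 is not randomized and is unaffected. The passages should be reconciled, but they do not show that unblinding will occur.

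**What to change.** Amend the Protocol Table 2 footnote, Protocol 5.3.1 and SAP Table 2 footnote j, with a cross-reference to SAP 7.6 and Protocol 4.4.1, to say that:

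- for randomized subjects (Groups 1 and 2), results for the 11 non-PCV13 serotypes and for SP1500+0785 do not reach blinded subjects or endpoint-assessing staff before database lock;
- any earlier release needed for the stated standard-of-care purpose goes only through staff who are already unblinded under Protocol 4.4.1 and do not assess endpoints;
- any report that does reach blinded staff has the same content in both arms.

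The cost is wording in two documents and an instruction to the laboratory vendor. Emergency unblinding is unchanged. The downside is that blinded site staff see these results later. The wait is longest for early enrollees, because lock follows the last subject's Day 180. How the standard-of-care use fits with this is for the sponsor to reconcile; no clinical rule is proposed here.
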